Title: Kovanaze Vs. Articaine in Achieving Pulpal Anesthesia of Maxillary Teeth

NCT #: NCT03962634

Document date: 08/28/2019

Document Type: Protocol and Statistical Analysis Plan

Kovanaze vs. Articaine in Achieving Pulpal Anesthesia of Maxillary Teeth: A Randomized, Open-label, Non-Inferiority Trial

Background:

The words a common man would associate with a dentist are 'pain', 'drill' and 'needle'. This association is unfortunate for dentists because a majority of dental procedures require local anesthesia to ensure patient safety and comfort. In clinical dentistry, local anesthetics are directly injected in various sites of the mouth.

Studies have shown that it is the psychological aspect of seeing the needle or expecting a needle to enter the mouth that scares most patients. From a patient's perspective, the needle has been identified as the most fear provoking part of the dentists' armamentarium. The sight of a sharp, metallic needle entering a protected part of the body greatly increases the anxiety and triggers the 'fight or flight' response. The resulting release of adrenaline might be as much as 40 times the normal levels. This adrenaline burst can result in syncopal episodes that accounts for more than half of medical emergencies in dental practice. Heart attacks and strokes can occur in patients suffering from cardiovascular diseases (hypertension, myocardial infarction, angina, arrhythmia). [1] It is recommended that more medically compromised the patient is, more efforts should be made to reduce anxiety. [2]

The aspirating syringe and needle used today was introduced around 150 years ago. [3] It is estimated that up to 40 million Americans avoid visiting the dentist because of fear of pain and anesthetic injections. [4-6] One study found most patients view the injection as the only painful part of the dental procedure. [7]

In June 2016, an intranasal delivery system of local anesthesia called Kovanaze, gained FDA approval. [8] Kovanaze is available as a 0.2 ml metered spray and is intended to achieve pulpal anesthesia of 5 maxillary teeth on either side of the face. Even though success rates between 83 and 90 % have been reported for adults and children >40kg, FDA label (Section 14.2) provides data for children (>10 kg) indicating that the drug is safe for use in children as long as the dose is adjusted to bodyweight of the child. [9]

- One 0.1 mL spray for patients weighing 10 kg to less than 20 kg;

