- Maximum blood pressure reading of 166/100 mmHg
- Vital pulp (Cold and EPT positive)

Exclusion Criteria:

- History of inadequately controlled hypertension or active thyroid disease
- Five or more nosebleeds in the past month
- Known allergy to oxymetazoline, tetracaine, benzylalcohol or para-aminobenzoic acid
- History of congenital or idiopathic methemoglobinemia
- Taking monoamine oxidase inhibitors, tricyclic antidepressants (e.g. amitriptyline), or non-selective beta adrenergic antagonists (e.g. propranolol)
- Taking oxymetazoline-containing products (i.e., Afrin) in the last 24 hours

- Pregnant and lactating women
- Non vital pulp (Cold and EPT negative)

Study Characteristics:

Design:

Randomized, open label clinical trial

Non-inferiority threshold and Sample size calculation:

The anesthetic efficiency of articaine has been reported in the literature to be around 78 – 88% (Evans et al.). The non-inferiority threshold is the maximum allowable excess of outcome events arising from the novel treatment compared with the standard treatment. The threshold for this study has been selected based on draft guidance set by the FDA (Temple et al.) and was set at 25%. Using nQuery Advisor v7.0, we verified that a sample size of 38 subjects per group would be needed to show a non-inferiority of <25% (one sided alpha of 0.05 and a power of 83%).

Accordingly, each of our study arms will have 90 subjects: 45 in Kovanaze and 45 in Articaine groups.

Accounting for screen failures and dropouts, we will recruit 100 participants in each population totaling 300 for the entire study.

Intervention:

Metered Kovanaze sprays (0.2 ml each spray, St. Renatus) in the nostril on the same side as the tooth of interest. The dose involves:

2 sprays in adult and kids weighing 40 kg or more

1 spray in kids > 6 years but weighing between > 20 kg and < 40 kg

Control:

- Children: 1.0 ml of 4% articaine (containing 1:100000 epinephrine) delivered in the periapex of the tooth of interest by labial/buccal infiltration
- Adults: 1.8ml of 4% articaine (containing 1:100000 epinephrine) delivered in the periapex of the tooth of interest by labial/buccal infiltration

Population:

Our study will evaluate the effectiveness of Kovanaze in three different populations.

Population 1: *Children (aged 6-17 years and weighing >20 kg) requiring specific procedures for treatment of oral disease*

Location: Department of Pediatric Dentistry, 3rd floor, Wood Building

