The biostatistician on the study team ([name]) will generate random sequence using a computer. The randomization will be in block of varying size (4 or 6) and the list will be provided to the following lead faculty who will serve as co-investigators as listed below:

Population 1: Pediatric Dentistry, [name]

Population 2: Endodontics, [name]

Population 3: General Practice, [name]

b. Allocation Concealment:

All random assignments will be placed in sequentially numbered opaque envelopes and will be handled by a staff in the respective department (not a part of the study team). If the participant is found to be eligible for the study, the resident/ student will inform the patient about the study. The team will answer all questions regarding the study and will request consent to participate in the study. After obtaining written patient consent, the department staff (not a member of the study team) will reveal the allocation.

Outcomes:

Patient important outcomes are considered including the primary outcome of completion of intended procedure without rescue anesthetic. This dichotomous outcome (success or failure of anesthesia) is linked to patients' rating of pain on a validated Heft-Parker visual analog scale. The emoji scale will be used for children. Group comparison between the articaine and Kovanaze formulations for anesthetic success will be analyzed by using Fisher's exact test.

Secondary outcomes include objective assessment of hard tissue and soft tissue anesthesia, anxiety scale (STAI-Y6 short form for children and MDAS scale for adults).

[figure not shown]
Adult participants who receive Kovanaze will also be asked to complete a survey to assess the impact of Kovanaze on patient confidence in seeking dental care.

Primary Outcome Measure in Adults:

Proportion of study participants in whom intended dental procedure could be successfully completed without the need for rescue anesthetic.

Heft Parker Scale: Each patient will rate his or her initial pain on a Heft Parker visual analogue scale, a 170-mm line with various descriptive terms. The subjects will be asked to place a mark on the scale where it best described their pain level both at the start and any time during the procedure. To interpret the data, the VAS is divided into the following four categories:

- a. No pain corresponded to 0 mm on the scale.

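### The primary analysis is a Fisher's exact test of equal success rates, which cannot test the 25-point non-inferiority margin the trial is sized on

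*Combined protocol and SAP*

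**What the plan says.** The title describes the study as "A Randomized, Open-label, Non-Inferiority Trial". The section on the non-inferiority threshold and sample size defines the margin ("The non-inferiority threshold is the maximum allowable excess of outcome events arising from the novel treatment compared with the standard treatment"), sets it at 25%, and reports that 38 subjects per group are needed to "show a non-inferiority of <25% (one sided alpha of 0.05 and a power of 83" percent). It then plans 45 per group in each population. The control success rate is given only as a range: "The anesthetic efficiency of articaine has been reported in the literature to be around 78 – 88" percent.

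The primary outcome is binary: the intended procedure is completed without rescue anesthetic. The Outcomes section gives one analysis for it: "Group comparison between the articaine and Kovanaze formulations for anesthetic success will be analyzed by using Fisher's exact test". The document states no shifted null hypothesis, no confidence interval for the difference in success, no comparison with the 25% margin, and no rule for concluding non-inferiority. The only other analysis mentioned for anesthetic effect is a subgroup analysis in the children's population, which is not specified.

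**The concern.** A non-inferiority trial has to reject the hypothesis that the new treatment is worse by the margin or more. Fisher's exact test, as normally run, tests whether the two success rates are equal. A non-significant Fisher result may only mean that the sample is small, so it does not show that a 25-point deficit has been excluded. A significant result against Kovanaze does not show that the deficit reaches 25 points.

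The stated 83% power and 5% one-sided error belong to a margin test that the plan does not run. Because the document is silent on how the Fisher result would be converted, the rule for the headline question would be chosen after the data are seen, in an open-label trial. The two obvious conversions both behave badly. Reading no significant difference as non-inferior inflates the false-claim rate. Requiring a significant result in favour of Kovanaze leaves almost no power.

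**Working it through.** **Inputs.** From the sample-size section: margin Δ = 0.25, one-sided alpha 0.05, power 83%, 38 per group needed, 45 per group planned, articaine success 78% to 88%. The rate actually used for sizing is not stated. The significance level and sidedness of Fisher's test are not stated either, so both two-sided 0.05 and one-sided 0.05 are shown.

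**Step 1: reproduce the plan's sample size.** For a non-inferiority test on the difference in proportions, with equal true rates p and unpooled variance:

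n per group = 2p(1−p)(z₀.₉₅ + z₀.₈₃)² / Δ²

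With p = 0.78: 2 × 0.78 × 0.22 × (1.645 + 0.954)² / 0.0625 = 37.1, rounded up to **38**. Power at n = 38: the standard error is √(0.3432/38) = 0.0950, and Φ(0.25/0.0950 − 1.645) = Φ(0.986) = **83.8%**. Both agree with the stated 38 and 83%. The 78% is inferred as the low end of the stated range; 83% or 88% in both groups would give 31 or 23. The trial is thus sized on an absolute 25-point margin.

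**Step 2: false-claim rate if a non-significant Fisher result is read as non-inferior.** Every possible pair of success counts was enumerated with exact binomial probabilities, with Kovanaze truly 25 points worse. The last column is the chance that the lower limit of the 90% Wald interval exceeds −25 points.

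| True success, articaine vs Kovanaze | n per group | Fisher two-sided p ≥ 0.05 | Fisher one-sided p ≥ 0.05 | Margin test (Wald) |
|---|---|---|---|---|
| 78% vs 53% | 45 | 35% | 25% | 4.8% |
| 83% vs 58% | 45 | 32% | 22% | 5.1% |
| 88% vs 63% | 45 | 27% | 17% | 5.1% |
| 78% vs 53% | 38 | 45% | 31% | 4.7% |
| 83% vs 58% | 38 | 40% | 29% | 5.0% |
| 88% vs 63% | 38 | 34% | 24% | 5.0% |

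The Farrington-Manning score test at 45 per group gives 5.1% to 5.3%.

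**Step 3: power if a significant Fisher result is required.** With equal true rates and 45 per group, two-sided Fisher is significant in either direction 2.4% to 2.6% of the time, and in favour of Kovanaze in about 1.3% of trials or fewer.

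**Step 4: single results on which the two methods part (45 per group).** The Wald lower limit is d − 1.645 × √[p₁(1−p₁)/45 + p₂(1−p₂)/45].

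- Kovanaze 32/45, articaine 39/45: d = −15.6 points, standard error 8.4 points, lower limit −15.6 − 13.9 = −29.4. Fisher two-sided p = 0.12. There is no significant difference, but non-inferiority is not shown.
- Kovanaze 39/45, articaine 45/45: d = −13.3 points, standard error 5.1 points, lower limit −21.7 (Newcombe −23.8). Fisher two-sided p = 0.026. Kovanaze is significantly worse, yet the margin is met.

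**Step 5: power of a margin test at the planned size.** With equal true rates of 78%, 83% and 88% and 45 per group, exact power at one-sided 0.05 is 88.9%, 93.5% and 97.6% (Wald limit), or 88.8%, 93.0% and 96.6% (Farrington-Manning).

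**The case against.** The strongest reply is that the sample-size section already holds most of a decision rule. A margin of 25% with a one-sided alpha of 0.05 implies the usual criterion that the one-sided 95% limit must exclude a 25-point deficit. On that view the Outcomes sentence names a test for a group comparison without calling it the non-inferiority decision, and the plan is incomplete rather than wrong. This does not rescue it. The document is the statistical analysis plan, it names one test for the primary outcome, and that test does not use the margin.

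Several narrower points do stand as qualifications:

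- A Fisher result significantly favouring Kovanaze would imply non-inferiority, so the planned analysis is not strictly incapable of supporting the claim. Under equal rates this happens in only about 1.3% of trials or fewer.
- The false-claim rates depend on a reading the document does not state. At one-sided 0.05, the only level the plan gives, they are lower than at two-sided 0.05, though still at least three times the intended 5%.
- The 39/45 versus 45/45 example needs no articaine failures. At 78% to 88% success, 45/45 has a probability of about 0.001% to 0.3%. The example shows the logic, not a likely event.
- The power match rests on an inferred 78% in both groups.

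**Conclusion.** The concern holds and must be fixed. The trial is titled and sized for non-inferiority at 25 points, and its only stated primary analysis tests equality. If non-significance were taken as non-inferiority at a true 25-point deficit, the false-claim rate at the planned 45 per group would be 27% to 35% with a two-sided test or 17% to 25% with a one-sided test, against about 5% for a margin test. These figures assume articaine success of 78% to 88%, an absolute margin, and a 0.05 level for Fisher's test. The existence of the defect depends on none of these assumptions. The fault is in the analysis and decision rule. The sample size is adequate for a margin analysis if the true success rates are equal.

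**What to change.** Replace the Fisher sentence in the Outcomes section with a rule along these lines: within each of the three populations, the difference in success proportions (Kovanaze minus articaine) will be estimated with a two-sided 90% score confidence interval, by a named method such as Miettinen-Nurminen or Farrington-Manning. Non-inferiority will be concluded if the lower limit is above −25 percentage points. Fisher's exact test may stay as a secondary test of difference, with its sidedness and level stated.

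The choice of a score interval is a preference; another valid interval would serve if it is named in advance. Separate conclusions by population follow from the per-population sizing, and the text should say so.

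The cost is one paragraph. The interval comes from the same 2×2 table and uses the margin and alpha already in the plan. No extra data or patients are needed.

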Eligible procedures: Procedures that would require local anesthesia include direct restorations (fillings), pulpotomy or pulpectomy (partial or complete removal of pulp) and placement of stainless steel crowns.

The standard of care in Department of Pediatric Dentistry is to administer nitrous before start of the treatment to alleviate patient anxiety. We will follow routine clinical protocol to titer the dose of nitrous oxide to individual patient needs.

Additionally, we hypothesize that the degree and depth of anesthesia would vary based on the initial disease state as well as the intended procedure. Accordingly, impact of the anesthesia will be analyzed at the completion of study using subgroup analysis.

Population 2: Symptomatic adults (>18 years) with symptomatic irreversible pulpitis

Location: Department of Endodontics, 2nd floor, Lyons Building

Eligible procedures:

Root canal treatment in teeth with significant decay but presenting with signs and symptoms of irreversible pulpitis (symptomatic)

Additional Inclusion Criteria:

- Tooth with a diagnosis of symptomatic irreversible pulpitis with or without periapical periodontitis
- Diagnosis is confirmed by history of spontaneous pain or prolonged (lingering) pain on application of cold or electronic pulp testing
- Tooth should have moderate to severe pain at the study onset (>54 on Heft Parker VAS scale)

Additional Exclusion criteria:

- Tooth with no response to cold / electronic pulp testing
- Tooth with periapical pathosis as seen in the radiograph
- Tooth with no vital coronal pulp tissue upon access

Population 3: Asymptomatic adults (>18 years) requiring restorations or crowns

Location: Department of General Practice, 2nd floor, Lyons/ Wood Building

Eligible procedures:

Direct and indirect restorations in teeth with significant decay but presenting with signs and symptoms of healthy pulp or reversible pulpitis

Additional Inclusion Criteria:

- Asymptomatic maxillary tooth with a diagnosis of primary or secondary dental caries extending more than 70% the thickness of dentin as seen in the radiograph

Additional Exclusion criteria:

- Tooth with no response to cold / electronic pulp testing
- Tooth with periapical pathosis as seen in the radiograph
- Endodontically treated tooth

Randomization

a. Sequence Generation:

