5. What is the most important deciding factor for you to choose NASAL SPRAY ANESTHETIC for your dental needs?

Cost Fear and Anxiety

6. How much extra money would you be willing pay for the NASAL SPRAY ANESTHETIC?

\$20 \$50 Up to \$100 It is not worth paying extra

7. Did your experience with the NASAL SPRAY ANESTHETIC change your outlook towards receiving future dental care?

Nothing changed; Still scared of dental visits This appointment was better but am still concerned about my future visits This appointment definitely eased my apprehension of future dental visits

8. If you had known that there was an option of NASAL SPRAY ANESTHETIC, would you have sought dental care early?

Definitely No Maybe Definitely Yes

5. Survey after 24 hours:

A short one question about the side effects of local anesthetic will be asked to the patient in person or over phone at 24 hours.

Did you suffer any of the following side-effects after your dental visit?

- nasal drainage,
- nasal congestion,
- burning,
- pressure,
- sinus congestion,
- pain and soreness at the site of the anesthesia (scored from 1-10)
- Numbing or tingling in throat
- other (Specify)_____

Flow of research study visit in adults (>18 years):

Screening of EHR will be done to identify potential study participants on a routine clinical visit. During the study visit the study related procedures would be preformed in the following order:

1. Go over the study details, answer participant questions and obtain informed consent
2. Administer MDAS anxiety survey
3. Ask patient to rate pain (if present) in the Heft Parker Scale
4. Reveal allocation (Kovanaze or Articaine)
5. Take baseline BP and heart rate
6. Administer local anesthetic
7. Wait for patient to signal achievement of meaningful anesthesia (using stop watch)
8. Map the extent of soft tissue and hard tissue anesthesia in data collection form
9. Proceed with the intended procedure
10. Assign anesthetic **failure** if subject perceives pain after start of procedure. Record the failure in data collection form and proceed with rescue anesthetic to complete the procedure
11. Assign anesthetic **success** if local anesthesia was adequate to complete the intended procedure without need for rescue anesthetic. Record in data collection form
12. Administer MDAS survey for all participants
13. Administer satisfaction questionnaire to subjects in Kovanaze group only
14. Take end of appointment BP and heart rate

Primary Outcome Measure in Children:

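### The primary test cannot use the pain score taken before allocation; in Population 2, adjusting for it may improve precision if baseline pain predicts success

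*Combined protocol and SAP*

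**What the plan says.** The Outcomes section names one analysis of the primary outcome: "Group comparison between the articaine and Kovanaze formulations for anesthetic success will be analyzed by using" Fisher's exact test. No adjusted analysis of that outcome appears anywhere. The adult endpoint is binary: "Proportion of study participants in whom intended dental procedure could be successfully completed without the need for rescue anesthetic". A Heft-Parker rating above 54 mm during the procedure counts as failure. (The documents word the boundary at 54 in more than one way; that does not affect this point.)

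The same scale is used at baseline: "Each patient will rate his or her initial pain on a Heft Parker visual analogue scale". In the adult visit flow, step 2 is "Administer MDAS anxiety survey", step 3 is "Ask patient to rate pain (if present) in the Heft Parker Scale" and step 4 is "Reveal allocation (Kovanaze or Articaine". The pain score is therefore fixed before anyone at the visit knows the arm.

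For Population 2 the additional inclusion criteria add: "Tooth should have moderate to severe pain at the study onset (>54 on Heft Parker VAS scale". The line is 170 mm long, so entry cuts off the lower part of the scale but leaves most of it open.

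The Randomization section describes blocks of 4 or 6 with a list for each population, and no stratification by baseline pain.

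**The concern.** Baseline pain in Population 2 is the same patient's rating on the scale that later decides success or failure, so it is a natural candidate for a prognostic covariate. Neither the randomization nor the primary analysis uses it. If it is prognostic, chance differences in baseline pain between two arms of 45 add avoidable noise to the success difference. That difference is the quantity to be judged against the 25-point margin. What is at stake is some precision and power in Population 2.

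**Working it through.** **1. The plan's own figure.** Inputs from the sample size section: margin 25 points (read as an absolute difference), one-sided alpha 0.05, power 83%, articaine success 78–88%, 38 per group. The rate used is not stated. With 78% in both arms (assumption) and unpooled variance:

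n = (1.645 + 0.954)² × 2 × 0.78 × 0.22 / 0.25² = 6.755 × 0.3432 / 0.0625 = 37.1, rounded up to 38.

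Power at 38 is Φ(0.25/0.0950 − 1.645) = 83.8%. The stated figure reproduces, for an unadjusted comparison.

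**2. Unadjusted precision at the planned size.** With 45 per arm, SE = √(2p(1−p)/45).

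- At 78%: SE 0.0873, one-sided 95% half-width 1.645 × 0.0873 = 14.4 points, power 88.8% with no true difference.
- At 70%: SE 0.0966, half-width 15.9 points, power 82.7%.

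**3. Effect of adjustment on variance.** The documents give no prognostic strength, so this is a range under assumptions: 45 per arm, one covariate uniform on 55–170 mm, no treatment effect. On that range 1 SD is (170 − 55)/√12 = 33 mm. Several thousand trials were simulated per scenario. Each was analysed by the raw difference and by a logistic model with arm and baseline score, standardised to a success difference. The table gives the ratio of adjusted to raw variance. Ranges show the spread between repeated runs, and the second decimal is uncertain by about 0.02.

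| Odds ratio per SD | 70% success | 78% success | 88% success |
|---|---|---|---|
| 1 | 1.01 | 1.01 | not tabulated |
| 1.25 | 1.00 | 1.00–1.01 | not tabulated |
| 1.5 | 0.98 | 0.98–0.99 | 0.99 |
| 2 | 0.93 | 0.93–0.95 | 0.98 |
| 3 | 0.82–0.83 | 0.84–0.85 | 0.90 |
| 4 | 0.73–0.75 | 0.77–0.80 | 0.88 |

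**4. What that means against the margin.** For a variance ratio r, half-width = 1.645 × SE × √r, power = Φ(0.25/(SE√r) − 1.645), and equivalent n per arm = 45/r. At 78% success:

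| r | Half-width (points) | Power | Equivalent n per arm |
|---|---|---|---|
| 1.01 (odds ratio 1) | 14.4 | 88.6% | 44.6 |
| 0.98 (1.5) | 14.2 | 89.4% | 45.9 |
| 0.93 (2) | 13.9 | 90.7% | 48.4 |
| 0.85 (3) | 13.2 | 92.8% | 52.9 |
| 0.77 (4) | 12.6 | 94.7% | 58.4 |

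At 70% success, r = 0.93, 0.83 and 0.73 give half-widths of 15.3, 14.5 and 13.6 points.

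**5. Chance imbalance.** The SE of the difference in mean baseline pain is √(2/45) = 0.21 SD, about 7 mm. At 70% success, an imbalance of 2 SE would move the raw difference by about 6 points at an odds ratio of 2, or about 8 points at 3.

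**The case against.** The strongest reply is that nothing here is wrong. Randomization makes the unadjusted comparison valid, and ordinary chance imbalance is already part of its error rate. The sample size was set for an unadjusted comparison, and 45 per arm exceeds the 38 required. All of that stands. A reader might infer that the Population 2 result is biased or underpowered because baseline pain is left out; the documents do not support that.

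A reader might also infer that the result is certainly less precise than it could be. That does not follow either. Baseline pain is rated before anesthesia and the outcome during the procedure after it, so a shared scale does not establish prediction. Entry above 54 mm also narrows the range. The only prognostic statement in the documents, on disease state and procedure, is made under Population 1 and leads to a subgroup analysis. At odds ratios up to 1.25 per SD the gain is nil or slightly negative, so adjustment is not free. With two covariates that carry no information, the variance rises by about 3%.

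Finally, the plan states no confidence bound for the success difference, and Fisher's exact test as written does not address the margin. That is a separate and larger gap; adjustment is a refinement to add once a bound is specified.

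What the reply leaves standing is an unequal trade: about 1% more variance if baseline pain carries no information, against 5–7% less at an odds ratio of 2 and 15–18% less at 3.

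**Conclusion.** The point holds as an improvement for Population 2, not as an error. The primary test cannot use a pre-allocation measurement on the outcome's own scale, so the valid unadjusted result may be less precise than the data allow if that measurement is prognostic. At 70–78% success the variance change runs from about +1% (odds ratio 1 per SD) through −2% (1.5), −5 to −7% (2) and −15 to −18% (3) to −20 to −27% (4). At 88% success the largest reduction is about 12%.

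These figures rest on an assumed uniform baseline and assumed success rates. The plan's 78–88% for articaine is not given for Population 2 specifically. The odds ratios are scenarios, not estimates.

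A reader might extend the argument to adjusting for MDAS in Population 3, because it too is recorded before allocation. The documents do not link dental anxiety to anesthetic success, and no calculation supports that step, so it is not part of this point.

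**What to change.** For Population 2, prespecify a logistic model for anesthetic success with arm and baseline Heft-Parker score as a continuous covariate. From it, report the standardised (g-computation) difference in success proportions with its one-sided 95% bound, and compare that bound with the 25-point margin. A conditional odds ratio would not be on the margin's scale. Name the variance method, for example the delta method or bootstrap, and what is done if the model does not converge. Keep the unadjusted difference with its own bound as a sensitivity analysis.

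Because the trial is open label, the covariate and model should be fixed before outcome data are examined.

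The cost is a few lines of SAP text and code. The score is already collected and is needed for entry to Population 2. The downside is about 1–2% of precision if baseline pain proves uninformative.

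### The plan sizes and allocates three populations separately, but its one primary analysis sentence does not say whether non-inferiority is decided per population, pooled or stratified, and gives no margin or rule for combining three results

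*Combined protocol and SAP*

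**What the plan says.** All references are to the combined protocol and SAP.

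- **Aim.** The Population section states: "Our study will evaluate the effectiveness of Kovanaze in three different populations". These are children, adults with symptomatic irreversible pulpitis, and asymptomatic adults needing restorations or crowns.
- **Sizing.** The section on the non-inferiority threshold and sample size sets a 25% margin and finds that "a sample size of 38 subjects per group would be needed to show a non-inferiority of <25"%, with "one sided alpha of 0.05 and a power of 83"%. It then says "each of our study arms will have 90 subjects: 45 in Kovanaze and 45 in Articaine groups". The next sentence recruits 100 per population and 300 in all, so a study arm of 90 here means a population.
- **Allocation.** Under Randomization, the list goes to a lead for each of the three populations, and the envelopes are held in each department. Separate lists are implied, although stratification is not named.
- **Outcome.** Success is defined under separate headings for adults and children, with different pain scales.
- **Analysis.** The one sentence on the primary comparison is in Outcomes: "Group comparison between the articaine and Kovanaze formulations for anesthetic success will be analyzed by using" Fisher's exact test.
- **Subgroups.** A subgroup analysis by disease state and procedure is mentioned under Population 1, with no method and no decision rule.

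**The concern.** The unit that was sized and allocated is the population. The analysis sentence refers only to the two formulations. A pooled, a stratified and a per-population analysis would all be consistent with it, and the choice could be made after the data are seen.

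The choice matters because the populations differ in disease, procedure, pain scale and control volume, and the protocol itself expects the depth of anesthesia to vary with disease state and procedure. If two populations do well and one does badly, a pooled result can meet the margin while the trial's stated question, effectiveness in each of three populations, has a different answer in one of them.

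The named test adds to the problem. Fisher's exact test addresses equality of the two success rates. It involves no margin, so it cannot deliver a non-inferiority decision under any of the three readings.

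**Working it through.** **Inputs.** From the sample size section: margin 25 points (read as an absolute difference), one-sided alpha 0.05, power 83%, 45 per group per population, and articaine success "The anesthetic efficiency of articaine has been reported in the literature to be around 78 – 88"%. The plan states no single planning rate and no Kovanaze rate for the calculation. I assume equal true rates and 45 evaluable patients per group.

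**1. The plan's own figure.** n per group = (z_alpha + z_power)² × 2p(1-p) / margin². At p = 0.78: (1.645 + 0.954)² × 2 × 0.78 × 0.22 / 0.25² = 6.755 × 0.3432 / 0.0625 = 37.1, rounded up to 38. Power at 38 is 83.8%. The stated 38 therefore reproduces as a single comparison at the low end of the stated range. Rates of 83% and 88% would give 31 and 23.

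**2. Masking, if the data were pooled and judged by a confidence limit.** Neither condition is stated in the plan, and the counts are illustrative. Wald limits are d ± 1.645 × SE, with SE = √(p₁(1-p₁)/n₁ + p₂(1-p₂)/n₂).

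| | Kovanaze | Articaine | Difference | SE | 90% CI |
|---|---|---|---|---|---|
| Each of two populations | 37/45 | 37/45 | 0.0 | 8.06 | -13.3 to 13.3 |
| Third population | 18/45 | 37/45 | -42.2 | 9.26 | -57.5 to -27.0 |
| Pooled | 92/135 | 111/135 | -14.1 | 5.19 | -22.6 to -5.5 |

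The pooled lower limit clears -25. The third population's whole interval lies beyond it.

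**3. Stratifying alone does not remove this.** With equal stratum sizes the Mantel-Haenszel risk difference is the mean of the three differences: (0 - 42.2 + 0)/3 = -14.1. Its SE is √(8.06² + 8.06² + 9.26²)/3 = 4.90, so the lower limit is -14.1 - 1.645 × 4.90 = -22.1. That also passes.

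**4. How often.** In 200,000 simulated trials per scenario, with control rates of 78% to 88%:

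| True differences (points) | Pooled test declares non-inferiority | Poor population passes its own test |
|---|---|---|
| 0, -30, 0 | about 88% to 96% | about 1.5% |
| 0, -40, 0 | about 70% to 82% | about 0.05% |

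**5. What per-population decisions would cost.** Power at 45 per group is Φ(0.25/√(2p(1-p)/45) - 1.645). The chance that all three pass is that power cubed.

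| True rate, both groups | Power per population | All three pass | n per group at alpha 0.05/3, power 83% |
|---|---|---|---|
| 78% | 89% | 70% | 53 |
| 83% | 93% | 82% | 43 |
| 88% | 98% | 93% | 33 |

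If any single claim counts as trial success, three unadjusted tests give a familywise error of up to 1 - 0.95³ = 14.3%.

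**The case against.** A reader might infer that the plan specifies a pooled test of 135 versus 135. It does not. No section says the populations will be combined, and the figure of 135 does not appear. The surrounding text fits separate comparisons at least as well: 38 per group is a single-comparison size, it is raised to 45 and applied population by population, and the adult and child outcomes have their own headings. Pooled, the same patients would give more than 99.9% power at equal rates, which would make the stated sizing hard to explain. This part of the objection stands, and it is why the point is an unstated decision rule and not a wrong one.

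The masking figures also need a confidence limit compared with 25 points, which the plan does not contain. On the counts in step 2, the pooled Fisher test gives two-sided p = 0.011, so a difference would be reported. That does not make Fisher's test a safeguard. With 24/45 in place of 18/45, pooled p is 0.08 while the third population is at -28.9 points (lower limit -44.3). Neither p-value says anything about the margin. In that milder case the third population fails to show non-inferiority, but its interval still includes -25, so a deficit beyond the margin would not be established.

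A reader might further infer that one population, such as irreversible pulpitis, is expected to fail. The documents give no success rates by population, so the example shows only what is possible.

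The planned subgroup analysis shows that heterogeneity was considered. Without a method or a decision rule, it does not settle how non-inferiority is decided.

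**Conclusion.** The concern holds as a gap in the primary decision rule. The sample size section treats each population as its own comparison, and allocation is handled the same way. The analysis sentence does not follow through: it leaves the level of the comparison open, uses no margin and says nothing about combining three results. This is more than missing detail, because the test as written cannot reach a non-inferiority conclusion at any level.

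The possible size is large but conditional. If the data were pooled and compared with 25 points, a population truly 30 points worse would be covered by an overall non-inferiority claim in roughly nine trials out of ten. This rests on the other two populations having no true difference, 45 evaluable patients per group, Wald limits and control rates of 78% to 88%. It should be resolved before the data are analysed.

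**What to change.** Replace the analysis sentence with the following.

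1. **Decision.** In each population, estimate the risk difference in success (Kovanaze minus articaine) and declare non-inferiority there only if the one-sided 95% lower confidence limit lies above -25 points.
2. **Combination rule.** State whether all three populations must pass, in which case no alpha adjustment is needed, or whether each is a separate claim. If any single claim counts as trial success, either control alpha across the three or report that the familywise error may reach 14.3%.
3. **Overall estimate.** If one is shown, use a Mantel-Haenszel risk difference stratified by population, give the arm-by-population interaction, and label it supportive. As step 3 shows, stratification does not prevent masking, so it should not carry the main conclusion.

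**Cost.** A few sentences and no new data. The trade-off is in power. Requiring all three to pass lowers the chance of overall success to about 70% at a true rate of 78%, against 89% for one population. Bonferroni control at the stated 83% power would need 53 per group at that rate. This exceeds the planned 45, and also the 50 per group that 100 recruits would give before losses. The stated power should be recalculated for whichever rule is chosen.
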